### 7.9.2. Change from baseline in mean total score

- *Computation of the Endpoint*

The change from baseline to each post-baseline visit will be computed as  $w - b$  where “w” is the post-baseline score and “b” is the score at baseline.

- *Analysis of the Endpoint*

Descriptive summaries, treatment group comparisons, and correlation analyses will be performed for change from baseline in mean total HSI score as described in Section 7.7.2. The covariance structure identified in Section 7.9.1 will be utilized.

### 7.10. Examination of Subgroups

Descriptive summaries will be prepared for the endpoints defined in Sections 7.3.2 (Percentage of WR recognized words) and 7.4.2 (Percentage of WIN recognized words) for the following subgroups using the FAS:

- Subject Demographics
  - Sex
  - Race

- Ethnicity
- Age (categories: 18 to <35, 35 to <50, 50 to 65, >65)
- Baseline Disease Characteristics
  - WR score at baseline (<50% versus ≥50%)
  - Etiology of hearing loss (SSNHL versus NIHL)

## 8. SAFETY EVALUATION

### 8.1. Overview of Safety Analysis Methods

The assessment of local and systemic safety of single and repeated doses of FX-322 in subjects with stable sensorineural hearing loss is an objective of this study. The safety analyses will be performed for the safety analysis set and will include treatment-emergent adverse events (TEAEs), serious adverse events (SAEs), clinical laboratory measurements, vital signs, physical examination, otoscopic examination, tympanometry, concomitant medications, and Columbia-Suicide Severity Rating Scale (C-SSRS) assessments. Tabular summaries of descriptive statistics will be presented for all subjects included in the Safety Analysis Set and subjects will be classified into actual treatment groups based on the actual number of FX-322 doses received in any ear (qualified or not qualified).

Where appropriate, treated will be distinguished from the untreated ear, as described in Section 3. For unqualified ears that receive study treatment in error, the date and time of the study drug administration, or date if time is missing, or visit if date is missing (except for ear-related AEs, as provided below), will be used to identify assessments that will be classified as treated for safety analyses by ear.

If an assessment occurs on the same date that an unqualified ear receives study treatment in error, and assessment time or treatment start time is missing, the assessment will be presumed to have occurred prior to study drug administration for purposes of defining the ear as treated (i.e., the ear would be considered untreated at that assessment), with the exception of ear-related AEs, in which case the ear would be considered treated. The same logic would be applied to assessments other than ear-related AEs if the assessment occurred on the same visit that an unqualified ear receives study treatment in error and one or both dates are missing. For ear-related AEs, partial dates will be imputed for purposes of identifying treated ears in the same manner they are for purposes of defining TEAEs, as provided below.

For all safety endpoints, baseline will be the last non-missing value before first administration of study drug.

For all shift from baseline analyses, percentages will be based on the number of subjects in each baseline category.

Safety data will not be imputed, except for partial and missing dates, which will be imputed only for defining TEAEs and concomitant medications. Imputed dates will not be presented in data listings.

Partial dates will be imputed for the purposes of defining TEAEs as follows:

- For a missing start day where the month and year are present, the start day will be set to the first day of the month, unless the following two conditions are met:
  1. the first day of the month is before the date of first administration of study drug and the month and year are the same as the month and year of the date of first administration of study drug, and
  2. the end date is on or after the date of first administration of study drug or the end date is completely missing.

If the two above conditions are met, the start day will be set to the day of first administration of study drug.

- For a missing start day and month where the year is present, the start day and month will be set to January 1st, unless 1) January 1st is before the date of first administration of study drug and the year is the same as the year of the date of first administration of study drug, and 2) the end date is on or after the date of first administration of study drug or the end date is completely missing, in which case the start day and month will be set to that of the date of first administration of study drug.
- For a missing end day where the month and year are present, the end day will be set to the last day of the month, unless the month and year are the same as the month and year of the last contact date for the subject, in which case the end day will be set to that of the subject's last contact date.
- For a missing end day and month where the year is present, the end day and month will be set to the subject's last contact date, unless the year of the subject's last contact date is greater than the end year, in which case the end day and month will be set to December 31st.

Partial and completely missing dates will be imputed for the purposes of classifying concomitant medications as follows:

- Partial dates will be imputed following the same algorithm as above for TEAEs.
- For an entirely missing start date (i.e., day, month, and year are missing), the start date will be set to the date of first administration of study drug unless the stop date is prior to the date of first administration of study drug, in which case the start date will be set to the stop date.

- For an entirely missing stop date (i.e., day, month, and year are missing), the medication will be treated as ongoing.

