For assessments completed by ear for each subject, the unit of analysis will be the ear and treated and untreated ears will be summarized separately. An ear will be considered treated from the time it receives any dose, whether the qualifying ear or not. A subject's treated ear will be classified into an actual treatment group based on the actual number of FX-322 doses received in that ear. An ear will be considered not treated up until the time it receives any dose, whether the qualifying ear or not. Untreated ears will be classified in the Placebo group up until the time it receives any dose, after which the ear will be classified into an actual treatment group based on the actual number of FX-322 doses received in that ear. Pre-dosing measurements will be mapped to treated or untreated based on dosing at Day 1. Subjects with treatment received in the non-qualified ear may contribute more than 1 treated ear to SfAS analyses. In the event that any subject/ear combination(s) receive 3 FX-322 doses, separate reports for subject/ear combination(s) receiving 3 FX-322 doses will be created, as applicable. Subject/ear combination(s) receiving 3 FX-322 doses will be included in the FX-322 total ears column.

For example, a subject treated with FX-322 2x in the qualified ear at Days 1 and 8 and treated with FX-322 2x in the not qualified ear at Days 15 and 21 will be summarized as follows:

- a. For summaries by subject: This subject will be included in the FX-322 4x section of the table.
- b. For summaries by ear:
  - i. The qualified ear data will be reported at all visits in the FX-322 2x section of the table in the Treated column.
  - ii. The not qualified ear data up to and including Day 15 will be reported in the Placebo section of the table in the Untreated column.
  - iii. The not qualified ear data after Day 15 will be reported at visits after Day 15 in the FX-322 2x section of the table in the Treated column.

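### Partial start dates of ear-related AEs are anchored on the subject's first dose, not the ear's, so some events after a wrong-ear injection are tabulated as untreated Placebo ears

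*SAP*

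**What the plan says.** Four parts of the SAP bear on this.

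- **Which rule applies.** Section 8.1 says: "For ear-related AEs, partial dates will be imputed for purposes of identifying treated ears in the same manner they are for purposes of defining TEAEs". It names no ear-specific date.
- **What that rule does.** For a missing day, Section 8.1 gives a default, "the start day will be set to the first day of the month", and an exception. The exception applies when "the first day of the month is before the date of first administration of study drug", the month and year match those of that dose, and the end date is on or after the dose or completely missing. In that case "the start day will be set to the day of first administration of study drug". A parallel rule for a missing day and month uses 1 January or the date of the first dose.
- **How the event is then classified.** Section 8.3 maps ear-related AEs in a wrongly dosed ear by when that ear was dosed. Section 3 fixes where an earlier event goes: "Untreated ears will be classified in the Placebo group up until the time it receives any dose". Its worked example shows the Untreated column of the Placebo section.
- **How doubt is meant to be resolved.** When an assessment falls on the same date as a wrong-ear injection and a time is missing, Section 8.1 presumes it came before the injection, "with the exception of ear-related AEs, in which case the ear would be considered treated".

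Wrong-ear dosing after Day 1 is foreseen: the Section 3 example has the unqualified ear injected at Days 15 and 21.

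**The concern.** The imputation uses one date and the classification uses another. The TEAE rule is built so that a doubtful event is placed on or after the first dose. It has that effect only for the dose it is anchored on. If the second ear is first injected one to three weeks later, both candidate dates (the 1st of the month and the subject's first dose) will usually fall before that injection, and the doubtful event is pushed to the untreated side. The same-day rule in the same section makes the opposite choice.

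Local safety is part of a primary objective, and Protocol Section 14.1.7.1 asks for ear events by treated and non-treated ear. The by-ear AE table is where an injection-related event should appear against an injected ear. Under the literal rule, some such events move to the column that represents ears never injected.

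**Working it through.** The SAP gives no figure for this, so there is none to reproduce. The check applies the written rules to dates.

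**Inputs from the SAP:** the start-date rules (Section 8.1); classification by the wrong-ear dose date (Section 8.3); dosing at Days 1, 8, 15 and 21.

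**Assumptions:** each date of one calendar year (2020) is equally likely as the first dose; the first wrong-ear dose is on the nominal day; true onset is uniform from that dose over a stated window; the AE end date is missing (an end date on or after the anchor dose gives the same result).

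**Worked dates, start day missing**

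| Subject's first dose | Wrong-ear dose | True onset | Imputed under SAP | Class | Imputed with the ear's own dose as anchor |
|---|---|---|---|---|---|
| 6 Jan | 20 Jan (Day 15) | 25 Jan | 6 Jan | Untreated | 20 Jan, treated |
| 20 Jan | 3 Feb (Day 15) | 10 Feb | 1 Feb | Untreated | 3 Feb, treated |
| 6 Jan | 20 Jan (Day 15) | 10 Feb | 1 Feb | Treated | 1 Feb, treated |
| 6 Jan | 6 Jan (Day 1) | 25 Jan | 6 Jan | Treated | 6 Jan, treated |

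In the second row the error comes from the 1st-of-month default rather than from the first-dose date. The cause is the same: the anchor is not the ear's dose.

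**General condition.** A missing-day event after a wrong-ear dose at Day 8, 15 or 21 is misclassified when it falls in the same calendar month as that dose and the dose was not on the 1st.

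**Hand check, 30-day month.** Let the wrong-ear dose fall on day k = 1 to 30 with equal chance, and let onset be uniform over n days starting that day. Then

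share = (1/30) × Σ(k = 2 to 30) min(n, 31 − k)/n.

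- Onset 0–1 days (n = 2): (28 + 1/2)/30 = 95%.
- Onset 0–7 days (n = 8): (22 + 28/8)/30 = 25.5/30 = 85%.
- Onset 0–14 days (n = 15): (15 + 105/15)/30 = 22/30 = 73%.
- Onset 0–30 days (n = 31): (435/31)/30 = 47%.
- Onset to Day 210 (n = 203, 196 or 190 for Day 8, 15 or 21): 435/(30n) = 7.1%, 7.4%, 7.6%.

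**Full calendar enumeration**

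| Onset window after wrong-ear dose | Day missing | Only year known |
|---|---|---|
| 7 days | 85.2% | 98.8% |
| 14 days | 73.8% | 97.8% |
| 30 days | 47.6% | 95.6% |
| To Day 210 | 7.3–7.8% | 72–74% |

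Among missing-day events in the same calendar month as the wrong-ear dose, 94–96% are misclassified. For a wrong-ear dose on Day 1 the figure is 0% throughout. With the ear's own first dose as anchor it is 0% in every scenario.

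**Price of the ear-specific anchor.** Missing-day AEs that truly began between Day 1 and the wrong-ear dose become treated in 87% (Day 8), 75% (Day 15) and 66% (Day 21) of cases, against 0% under the present rule.

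**Direction.** On the dosing schedule, a Day 8 injection is FX-322 in 2 of 4 groups, and a Day 15 or Day 21 injection in 1 of 4. Over the 12 group-by-visit cells that is 2 + 1 + 1 = 4 FX-322 and 8 placebo. No group goes from placebo to FX-322, so an ear first injected with placebo receives no FX-322 later under the schedule.

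**The case against.** **The anchor may be meant per ear.** Borrowing the TEAE method for the purpose of identifying treated ears could mean the same logic applied to that ear's dose. This is a fair reading, but no sentence says so. The only anchor written down is the first dose of study drug, and a programmer following the text would use the subject's first dose.

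**The rule does not fail for every injection after Day 1.** A reader might infer that it works only when the wrong ear was injected at Day 1. That is not so. Missing-day AEs in any later calendar month are imputed to the 1st of that month and correctly classed as treated, which is why the error falls to 7–8% over follow-up to Day 210. The short-window figures should not be quoted without that one.

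**It need not favour FX-322.** A reader might also infer that the rule makes FX-322 look safer than placebo. The documents do not support this in general. If errors were equally likely across groups and visits, 8 of 12 such injections would be placebo. The event would then stay in the Placebo section and move only from Treated to Untreated, which if anything makes injected placebo ears look better. Where the injection was FX-322, the event does leave an FX-322 group.

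**Other data limit the harm.** Otoscopy is scheduled before injection at each treatment visit and again at Days 60, 90, 150 and 210 (Protocol Section 12.1.7). It is summarised by ear using examination timing (SAP Sections 8.1 and 8.6.3), so a perforation seen at a later examination is still shown against a treated ear. By-subject TEAE and AESI tables do not use this rule, and all AEs are listed. These points stand, but they do not correct the by-ear AE table.

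**Occurrence is probably rare.** It needs a wrong-ear first dose after Day 1, an ear-related AE, and a partial start date left unresolved although onset dates are required (Protocol Section 13) and missing data are queried (Protocol Section 15.3). This is accepted.

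**Conclusion.** The point holds as a minor defect in a stated rule. Read literally, SAP Section 8.1 imputes with the subject's first dose while Section 8.3 classifies by the ear's dose. The result contradicts the SAP's preference for counting doubtful ear-related AEs as treated.

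Its scope is narrow: by-ear AE summaries, for ears first injected in error after Day 1, where the AE has a missing start day in the month of that injection or only that year is known. The percentages are conditional on such an event existing and rest on the assumed uniform dose dates and onset. How many such events there are cannot be learned from the documents. What is biased is the comparison of injected with uninjected ears; a bias of FX-322 against placebo is not established.

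**What to change.** In SAP Section 8.1, state that for identifying treated ears the partial-date algorithm is applied with the first dose of any study treatment in that ear as the anchor:

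- If the known month and year (or the known year, when only the year is recorded) are those of that injection, and the end date is missing or not before it, set the start to the injection date.
- If the known month is later, keep the 1st-of-month default. It already gives treated, and moving the event back to the injection would contradict a recorded month.

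Also amend the later sentence in Section 8.1 that restricts date imputation to TEAEs and concomitant medications, since the treated-ear use falls outside it.

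The cost is a sentence or two and a small derivation change, with no new data. The known downside is that most missing-day AEs that began after Day 1 but before the wrong-ear injection (66–87% with the end date missing) will be classed as treated. That is the cautious direction Section 8.1 already takes for same-day events, and an event with a recorded end date before the injection stays untreated.

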## 8.2. Extent of Exposure

The distribution of actual FX-322 doses received by randomized treatment group will be summarized as the number and percentage of subjects receiving 0, 1, 2, 3, or 4 doses of FX-322 in any ear and separately, in the qualifying ear to be treated. The summary will be by randomized treatment group and overall for subjects in the FAS.

The number and percentage of subjects receiving study treatment at each treatment visit (Day 1, 8, 15, 21) per the randomized treatment schedule in the qualifying ear to be treated will be summarized by randomized treatment group and overall for subjects in the FAS. The qualifying ear to be treated (Left Ear or Right Ear) will be captured on the Targeted Hearing Loss History CRF page and is the ear to be treated at all four treatment visits.

The number and percentage of subjects receiving incorrect study treatment at each treatment visit in the qualifying ear to be treated will be summarized by randomized treatment group and overall for subjects in the FAS.

The number and percentage of subjects treated in the non-qualifying ear at each visit will be summarized by randomized treatment group and overall for subjects in the FAS.

Dosing interval patterns for the qualifying ear each treatment group will be evaluated using the duration of days between each study treatment administration at Days 8, 15 and 21. The number of days between the current treatment administration and the prior treatment administration will be computed. The duration of days between each study treatment administration will be summarized categorically (<2 days, 2-4 days, 5-7 days, 8-10 days, >10 days) by treatment group and overall for the qualifying ear for subjects in the FAS.

If there are any dosing administrations errors such that a not qualified ear is treated, a sensitivity analysis may be performed summarizing the dosing interval patterns for any ear. Study treatment administration at each treatment visit will also be listed for subjects in the FAS; this listing will include actual treatment administered in each ear actually treated.

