#### **14.1.3 Analysis Sets**

- Full Analysis Set (FAS)

The Full Analysis Set is defined as all randomized subjects who receive at least one dose of study drug. Subjects will be analysed according to their randomized treatment group. The FAS will be used to explore efficacy. Details will be provided in the SAP.

- Per Protocol Analysis Set (PPAS)

The Per Protocol Analysis Set is defined as subjects receiving all four doses of study drug or placebo and without major protocol deviations that could interfere with interpretation of the results. These major protocol deviations will be identified prior to breaking the study blind. If different from the FAS, the PPAS may be used in additional sensitivity analyses. PPAS subjects will be analysed according to their randomized treatment group. Details will be provided in the SAP.

- Safety Analysis Set (SfAS)

The Safety Analysis Set will include all subjects exposed to study drug or placebo and will be analyzed according to the actual treatment group regardless of their randomized treatment assignment. The SfAS will be used for the analysis of safety. Both the treated and untreated ear will be included in the SfAS when the ear is the unit of the safety analysis.

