#### 4. ANALYSIS SAMPLES

The following definitions will be used to derive the analysis sets for this study.

- Full Analysis Set

The Full Analysis Set is defined as all randomized subjects who receive at least one dose of study drug (regardless of whether a full dose was administered) in the qualified ear per the

randomized treatment schedule. Subjects will be analyzed according to their randomized treatment group, as described in Section 3. For assessments completed by ear for each subject, treated (qualified) and untreated (not qualified) ears will be summarized separately, as described in Section 3. The FAS will be used to explore efficacy.

- Per Protocol Analysis Set

The Per Protocol Analysis Set is defined as subjects receiving all four doses of study drug or placebo in the qualified ear to be treated per the randomization treatment schedule and without major protocol deviations that could interfere with interpretation of the results. These major protocol deviations will be identified prior to breaking the study blind for the IA. Protocol deviations that occur after unblinding for the IA will be evaluated for major/minor classification by the blinded medical and study team prior to breaking the study blind for the CSR. If different from the FAS, the PPAS may be used in additional sensitivity analyses for efficacy. PPAS subjects will be analyzed according to their randomized treatment group, as described in Section 3. For assessments completed by ear for each subject, treated (qualified) and untreated (not qualified) ears will be summarized separately, as described in Section 3.

- Safety Analysis Set

The Safety Analysis Set will include all subjects exposed to study drug or placebo in any ear and will be analyzed according to the actual treatment group regardless of their randomized treatment assignment, as described in Section 3. For safety assessments by subject, the total number of FX-322 received in any ear will be used to assign actual treatment group. For safety assessments completed by ear for each subject, treated and untreated ears will be summarized separately, as described in Section 3. The SfAS will be used for the analysis of safety.

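### Three exposure outputs in SAP 8.2 use a Full Analysis Set that omits anyone injected only in the non-qualified ear, so their wrong-ear record is incomplete

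*SAP*

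**What the plan says.** SAP 4 defines the Full Analysis Set (FAS) as "all randomized subjects who receive at least one dose of study drug (regardless of whether a full dose was administered) in the qualified ear", following the randomized schedule. The Safety Analysis Set (SfAS) is wider: "all subjects exposed to study drug or placebo in any ear". Protocol 14.1.3 puts no ear condition on the FAS: "The Full Analysis Set is defined as all randomized subjects who receive at least one dose of study drug".

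SAP 8.2 then assigns the FAS to its exposure outputs. Three of them matter here:

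- **Dose distribution.** Subjects are counted by FX-322 doses received (0 to 4), once for any ear and once for the qualifying ear. "The summary will be by randomized treatment group and overall for subjects in the FAS".
- **Wrong-ear table.** It counts "subjects treated in the non-qualifying ear at each visit will be summarized by randomized treatment group and overall for subjects in the FAS".
- **Listing.** "Study treatment administration at each treatment visit will also be listed for subjects in the FAS". It is to show what was given in each ear that was actually treated.

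The other 8.2 tables with a stated population concern the qualifying ear only: treatment per schedule, incorrect treatment and dosing intervals. They also use the FAS. An any-ear dosing-interval sensitivity analysis is optional and has no stated population.

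The adverse-event tables in SAP 8.3 use the SfAS. The interim package in SAP 10 has the same pairing: exposure on the FAS, adverse events on the SfAS.

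**The concern.** A table that counts wrong-ear injections is built on a population whose entry rule requires a right-ear injection. The subjects it drops are those for whom the error was complete. The any-ear dose distribution has the same problem: it counts doses in either ear, but only for subjects who had at least one dose in the intended ear.

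The SAP expects wrong-ear dosing. Section 3 has rules for reclassifying ears and a worked example, and the efficacy sections plan sensitivity summaries for it. At stake is whether the exposure record matches the safety denominators. A reader could see an adverse event from an exposed subject in the SfAS tables and find no line for that subject in the listing of what was injected, where and when.

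**Working it through.** The plan states no figure on this point, and the sample size has no formal basis, so there is nothing to reproduce. The check is one of set membership.

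**Inputs.** There are four treatment visits (Protocol 8.7.3). A missed treatment is not made up (Protocol 8.8.3). The FAS and SfAS rules come from SAP 4, and the output populations from SAP 8.2.

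**Rules.** Code each visit as Q (qualified ear injected), N (non-qualified ear injected) or M (missed). FAS membership needs at least one Q. SfAS membership needs at least one Q or N.

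**Enumeration of ear patterns.**

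| | No missed visits | Missed visits allowed |
|---|---|---|
| All patterns | 2^4 = 16 | 3^4 = 81 |
| In SfAS | 16 | 81 − 1 = 80 |
| In FAS | 16 − 1 = 15 | 81 − 2^4 = 65 |
| With any wrong-ear injection | 16 − 1 = 15 | 81 − 2^4 = 65 |
| Of these, outside the FAS | 1 | 2^4 − 1 = 15 |
| Of these, kept by the FAS | 14 of 15 | 50 of 65 |

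The patterns lost are exactly those in which every injection received went to the non-qualified ear. A subject in the FAS can have at most three wrong-ear injections, so the FAS outputs can never show a subject with four. These are counts of patterns, not probabilities.

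**The shortest route.** The pattern N, M, M, M is among the 15. Protocol 8.4.4 and 9.1 ask subjects who stop study drug to stay in follow-up, so such a subject can contribute months of safety data.

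**Which 8.2 outputs are affected.** A subject dosed only in the wrong ear has no qualifying-ear dose. The subject cannot enter a numerator in the treatment-per-schedule or incorrect-treatment tables and has no qualifying-ear dosing interval, so at most a denominator moves. The any-ear dose distribution, the wrong-ear table and the administration listing do lose information.

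**What other outputs hold on such a subject.**

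| Output | Population | What it shows |
|---|---|---|
| SAP 5.1 disposition | Randomized subjects as denominator | Subjects treated at each visit; counts in each analysis set |
| SAP 6.1 deviation listings | Randomized subjects | Date, text and type of deviation |
| SAP 3 and 8.3 safety tables | SfAS | Grouping by actual FX-322 doses, by subject and by ear |

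None is specified to give the number injected in the wrong ear at each visit, or the product given in each ear at each visit.

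**Size of one case.** 1/24 = 4.2% of a planned arm; 1/96 = 1.0% of the planned study.

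**After the change.** On all randomized subjects with any injection, 15 of 15 and 65 of 65 wrong-ear patterns are shown.

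**The case against.** The strongest reply is that these subjects remain visible. Disposition reports treatment by visit on randomized subjects. It also gives FAS and SfAS counts by randomized group, and among randomized subjects the gap between the two is essentially this group. Deviations are listed for all randomized subjects, and the safety tables group each treated ear by the FX-322 doses it received. All of that stands. A reader might infer that these subjects vanish from the report, or that their injections are shown as zero. Neither is right: they are omitted from three outputs and present in others. What the reply does not supply is the wrong-ear count by visit or the ear-level listing.

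A reader might also infer that a wrong ear would tend to repeat because the ear is recorded once and used at all four visits. The documents do not support this. Under SAP 8.2 the recorded ear is the qualifying ear. If the wrong side were recorded and then injected, those doses would count as qualifying-ear doses and the subject would stay in the FAS. Exclusion needs every injection received to contradict the recorded ear. Mixed errors, including the SAP's own example of two doses in each ear, stay in the FAS and are shown.

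On the changed FAS definition, Protocol 14.1.3 leaves details to the SAP, and the SAP version history mentions the handling of treated and untreated ears for FAS analyses. So the ear handling is partly disclosed. Neither place says that the set was narrowed, and SAP 11 lists only the dropped multiplicity adjustment.

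**Conclusion.** The point holds for three outputs and one kind of subject: someone whose every injection went to the non-qualified ear. For that subject the any-ear dose distribution, the wrong-ear table and the administration listing are incomplete by definition, while the adverse-event tables include the subject.

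The practical size is small. Such subjects should be rare. The documents give no wrong-ear rate, so no figure for understatement can be given beyond the share that one subject represents (4.2% of a planned arm, 1.0% of the study). No efficacy estimate, adverse-event count or SfAS denominator is affected, and the study is exploratory. It is still worth correcting, because the rule guarantees an incomplete count in the table meant to supply it.

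The conclusion reads the FAS condition as one about the ear. SAP 4 also refers to the randomized schedule. If that was meant to require the correct product as well, a subject given the wrong product in the qualified ear at every visit would also leave the FAS, and with it the incorrect-treatment table. The text is ambiguous, and the point does not depend on that reading.

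**What to change.** In SAP 8.2, change the population of the any-ear FX-322 dose distribution, the non-qualifying-ear table and the administration listing from the FAS to all randomized subjects who received any injection in either ear. Keep the display by randomized group. Make the same change to the matching interim exposure output in SAP 10.

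This population fits better than the SfAS shown by randomized group, because SAP 3 groups SfAS tables by actual treatment. The qualifying-ear tables (treatment per schedule, incorrect treatment, dosing intervals) can stay on the FAS. Where any-ear and qualifying-ear counts share a table, state the denominator of each.

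As a minor addition, record in SAP 11 that the SAP adds a qualified-ear condition to the FAS of Protocol 14.1.3.

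The cost is a few lines of SAP text and one population flag in the exposure programs. Data collection does not change.
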